Official Title:

Effect of different labor analgesics on maternal UtA, fetal UA and MCA blood flow index observed by Doppler ultrasonography: A prospective randomized double-blinded controlled trial

Document Date:

March 1, 2021

Study protocol

1. Study design

Pregnant women of ASA grade I to II, aged 20 to 35 years, weighing 50 to 100 kg, 150-175 cm in height, and 37 to 41 weeks of gestation were included in the study. Women with contraindications of spinal anesthesia, maternal complications (such as pregnancy-induced hypertension, preeclampsia, cardiovascular and cerebrovascular diseases, etc.), abnormal uterine contractions, abnormal placental function or position, signs of fetal distress, and known fetal malformations were excluded. The patients who were failed to administer combined spinal and epidural block analgesia, those who were transferred from vaginal trial labor to cesarean section, those who could not cooperate with ultrasound detection, and those who needed to use oxytocin were excluded. The study was planned and implemented in accordance with the Declaration of Helsinki.

2. Randomization and blinding

90 parturients in the study were randomly assigned to Sufentanil group (S, n=30), Ropivacaine group (R, n=30) and Sufentanil added to Ropivacaine group (SR, n=30) by non-blind personnel according to the computer random number table, and the allocation was hidden. The solution was prepared by an unblinded anesthesiologist and packaged in a blind way and administered by another anesthesiologist. The patients, anesthesia providers, data recorders, ultrasound examiners, obstetrical staff, and nursing staff remained blinded to group assignment throughout the study.

3. Study intervention

At the time of request for labor analgesia, patients were randomized to receive either sufentanil 5 µg (Group S), ropivacaine 3mg (Group R), or sufentanil 2.5 µg added to ropivacaine 2.5 mg (Group SR) into the subarachnoid space. All groups received the standard epidural solution that contained 0.1% ropivacaine with 0.25 µg/ml sufentanil. Routine obstetric and anaesthetic monitoring was given after maternal entered the delivery room.

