placed on fetal head area. Middle cerebral arteries (MCA) run anteriorly on both sides of the ring of cerebral arteries at the position of the double head diameter (see Figure 1A). We can get waveforms of MCA examined by pulsed wave doppler (see Figure 1B). The probe was placed at the placenta area, and we can see the fetal umbilical cord connecting to the center of the placenta. Umbilical artery (UA) could be identified by color flow, and its waveforms were examined by pulsed wave doppler (see Figure 1C and 1D). The probe was placed at the midpoint of the groin. The right and left uterine arteries (UtA) could be identified by color flow at the apparent crossover with the external iliac arteries, and pulsed wave doppler was used to obtain waveforms (see Figure 1E and 1F). 3 to 10 arterial spectrograms with clear edges and no background noise at baseline were selected. The above arterial blood flow indexes were measured three times and the average value was taken. The S/D、PI、RI value of MCA、UA、UtA can be measured automatically by ultrasound instrument. All doppler examinations were performed by the same sonographer.

5. Primary outcomes

The main indexes were doppler blood flow indexes (S/D, PI, RI value) of UtA, UA, MCA before analgesia (T_0) and 30 min (T_1), 60min (T_2), 90 min (T_3) after analgesia in the three groups.

6. Secondary outcomes

Fetal heart rate (FHR) and mean artery pressure (MAP) at T_0 , T_1 , T_2 and T_3 , neonatal weight, time of each stage of labor, rate of midwifery, neonatal umbilical artery blood gas index and Apgar score at 1 min, 5 min, 10 min after birth of the three groups were included in the secondary indicators.

7. Statistical Analysis Plan

In this study, SPSS 13.0 was used for statistical analysis, and GraphPad Prism 8 was used for mapping. Measurement data were expressed as mean \pm standard deviation ($\bar{x}\pm s$), and categorical data were expressed as frequency, percentage, or rate. Paired t

test was used for intra-group comparison and independent sample t test was used for inter-group comparison of measurement data conforming to normal distribution. The measurement data with non-normal distribution were analyzed by rank sum test. Chi-square test was used for statistical analysis of categorical data. $P < 0.05$ indicates statistical significance.

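### Section 7 compares three arms with a two-sample t test at P<0.05 and no overall test, so each normally distributed secondary outcome carries about a 12% false-positive rate instead of 5%

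*Combined protocol and SAP*

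**What the plan says.** Section 2 sets up three arms: "90 parturients in the study were randomly assigned to Sufentanil group (S, n=30), Ropivacaine group (R, n=30") and a combination group, SR, also of 30.

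Section 6 gives the secondary outcomes. It begins with "Fetal heart rate (FHR) and mean artery pressure (MAP) at T_0 , T_1 , T_2 and T_3 , neonatal weight" and goes on to the labour and neonatal measures: "neonatal weight, time of each stage of labor, rate of midwifery, neonatal umbilical artery blood gas index and Apgar score at 1 min, 5 min", with a third Apgar score at 10 minutes. It does not give the number of labour stages or the blood gas components.

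Section 7 sets out the between-group tests by type of data:

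- Normal measurement data: "independent sample t test was used for inter-group comparison of measurement data conforming to normal distribution".
- Non-normal measurement data: "The measurement data with non-normal distribution were analyzed by rank sum test".
- Categorical data, with the one threshold for everything: "Chi-square test was used for statistical analysis of categorical data. $P < 0.05$ indicates statistical significance".

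Section 7 names no analysis of variance or other overall three-arm test, no multiplicity adjustment, no order among the secondary outcomes, and no statement that they are supportive or exploratory.

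**The concern.** An independent-sample t test compares two groups. With three arms, one outcome gives three comparisons (S with R, S with SR, R with SR). If each is judged at P<0.05 with nothing in front of it, the error rate for that outcome is well above the 5% that the threshold suggests. A chi-square test can take all three arms in one table, so the same P<0.05 may mean different error rates for different secondary outcomes.

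Section 6 holds the trial's only outcomes on maternal haemodynamics, the course of labour and the condition of the newborn. Under the rule as written, a single pairwise P<0.05 on a cord blood value or one stage of labour would be reported as a significant difference between spinal regimens. The reader would have no statement of how often such results arise by chance. Adjusting or ranking the primary Doppler indexes alone would leave these outcomes untouched.

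**Working it through.** The plan states no family-wise error rate, power or sample-size derivation, so there is no figure of its own to reproduce.

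**Inputs from the documents.** Three arms of 30 (section 2); two-sample t test and a threshold of 0.05 (section 7); outcome list (section 6).

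**Assumptions.** Two-sided tests; three labour stages; one to five blood gas analytes; normal data with a common correlation between outcomes; no true difference between arms.

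**Step 1: one normally distributed outcome.** There are 3 pairwise tests. Were they independent, the chance of at least one false positive would be 1 − 0.95³ = 0.143. They share arms, so the true value is lower: simulation with 30 per arm gives 0.118 to 0.123 in separate runs, or about 12%. If pairs are examined only after an overall ANOVA with P<0.05, simulation gives 0.048 to 0.049.

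**Step 2: number of secondary outcomes.** Baseline (T0) values and neonatal weight are left out, as are the paired within-group tests, so the count is on the low side.

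- Fetal heart rate and mean arterial pressure at T1 to T3: 2 × 3 = 6
- Labour stages: 3
- Rate of midwifery: 1
- Apgar scores: 3
- Blood gas: 1 to 5

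Total: 14 to 18. If all are tested pairwise, that is 42 to 54 tests and 0.05 × 42 = 2.1 to 0.05 × 54 = 2.7 expected false positives. If rate of midwifery and the three Apgar scores each have one three-arm test, it is 3 × 10 + 4 = 34 to 3 × 14 + 4 = 46 tests, and 1.7 to 2.3 expected.

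**Step 3: chance of at least one false P<0.05 across outcomes.** With independent outcomes, 1 − (1 − 0.12)^14 = 0.83 and 1 − (1 − 0.12)^18 = 0.90. Simulation (3,000 runs per setting, three t tests per outcome) gives:

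| Outcomes | correlation 0 | 0.3 | 0.5 | 0.8 |
|---|---|---|---|---|
| 10 | 0.73 | 0.66 | 0.55 | 0.37 |
| 14 | 0.84 | 0.77 | 0.67 | 0.41 |
| 18 | 0.90 | 0.83 | 0.72 | 0.43 |

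Repeat runs agree to within about 0.02, which gives 0.65 to 0.72 at correlation 0.5 for 14 to 18 outcomes.

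**Step 4: dependence on the form of test.** With rate of midwifery as one 2×3 chi-square test (10% rate assumed), each tied Apgar score under one Kruskal-Wallis test (distribution assumed) and pairwise t tests for the rest, 14 outcomes give 0.78 at correlation 0, 0.59 at 0.5 and 0.42 at 0.8.

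**Step 5: what an overall test per outcome achieves.** With exactly three arms, gating the pairs protects each outcome in both null situations. If all arms are equal, no pair is reached unless the overall test rejects, at 5%. If one arm differs, only one true null pair remains, tested at 5% (simulated 0.046 to 0.049). Across 14 to 18 outcomes, however, about 0.37 to 0.40 remains at correlation 0.5. At independence it is 1 − 0.95^14 = 0.51 to 1 − 0.95^18 = 0.60.

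**The case against.** The strongest reply is that unadjusted secondary outcomes are common where no confirmatory claim rests on them, and that this plan makes none: it says only what counts as statistically significant. It also already places these outcomes below the main Doppler indexes. Both points stand. They bear on error across outcomes, but do not answer the 12% on a single outcome.

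A reader might infer three stronger things that the documents do not support.

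- That every secondary outcome is tested pairwise. This follows only for normally distributed measurements, because the t test takes two groups. The rank sum and chi-square tests could be two-group or three-arm.
- That a chance finding somewhere in section 6 is more likely than not. This holds at moderate correlation under pairwise testing. It fails at a common correlation of 0.8 and, at correlation 0.5, with one overall test per outcome.
- That a false result on any particular outcome, such as the 1-minute Apgar score, is to be expected. The chance for one normally distributed outcome tested pairwise is about 12%.

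It can also be objected that an overall test does not control error across outcomes, and that Holm would be costly. For one arm differing by 0.8 SD, power of the overall test falls from 0.89 at 0.05 to 0.60 at 0.05/14; for 0.5 SD it falls from 0.49 to 0.16. This is a good reason not to impose Holm on outcomes that describe maternal and neonatal condition.

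Finally, the same section 7 sentences govern the primary indexes, so an overall-test rule written for all measurement data would reach both sets. That makes the change easier; it does not remove the need for it.

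**Conclusion.** The point holds for the error rate per outcome. For each normally distributed secondary outcome, the rule in section 7 gives about a 12% chance of a false significant difference where its threshold suggests 5%. This rests on the three arms, the named test and the absence of an overall test, with two-sided testing assumed.

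The figure across outcomes is less firm. At 14 to 18 outcomes all tested pairwise, it is about 0.65 to 0.72 at correlation 0.5, with a range from about 0.41 (correlation 0.8) to 0.90 (correlation 0). It depends on the assumed outcome counts, correlation and form of test, and on no true differences between arms. It shows that isolated secondary P values need cautious wording, not that a chance finding is assured.

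Nor should it be read as saying that the outcomes have no rank at all: they rank below the primary set, and only an order among themselves is missing. The trial's primary conclusion is not affected by this point.

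**What to change.** In section 7:

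1. For each secondary outcome, make one overall three-arm test first: one-way ANOVA for normal measurements, Kruskal-Wallis for non-normal ones, and a 2×3 test for rate of midwifery. Examine pairs only if it has P<0.05. This also settles whether the rank sum and chi-square tests are three-arm.
2. Report between-arm differences with 95% confidence intervals for every secondary outcome, whatever the P value.
3. State that isolated secondary P values are supportive, not confirmatory, because step 1 does not control error across outcomes.
4. Only if the sponsor wants a confirmatory claim on a secondary outcome, apply Holm to the overall-test P values across the section 6 outcomes, accepting the loss of power.

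The cost is a few sentences in the plan and routine SPSS procedures, with no extra patients or data. The downside is that some isolated pairwise results could no longer be called significant.

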An experienced the anesthesiologist select L3-4 lumbar vertebra clearance to puncture with standard sterile technique using loss of resistance when the puerpera palace has expanded to about 3 cm. After the puncture reached the epidural space, a 25-gauge lumbar anesthesia needle was used to puncture into the subarachnoid space. 2 mL of anesthetic drug as determined by her group randomization were administered into the cavity through the lumbar anesthesia needle after cerebrospinal fluid flow out. A 19-gauge spring-wound catheter was threaded 4-6 cm into the epidural space. All patients received a test dose of 3 ml of 1.5% lidocaine followed by an initial loading dose of 5 ml of the standard epidural solution. Epidural catheters into vessels or subarachnoid space were excluded. An analgesic pump (PCEA pump, 100ml) containing standard epidural solution was then connected to the epidural catheter at a background continuous infusion rate of 5 mL/h. The visual analogue score for pain (VAS) was performed 15 minutes after the injection dose, and if the VAS score fell below 3, the case was included in the study.

An anesthesia provider assessed the adequacy of analgesia for the patients throughout the duration of labor. Any breakthrough pain was managed with a physician-administered epidural bolus. All obstetric analgesia procedures were performed by the same anesthesiologist to reduce errors due to technical reasons.

4. Ultrasonic examination method

The patients were placed in a supine position with calm breathing to perform doppler ultrasonography during the interval of contractions. Ultrasound probe was

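### Section 7 tests within-arm change and between-arm difference under one P<0.05 rule without saying which answers the title question, and a within-arm change cannot be attributed to the allocated intrathecal drug.

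*Combined protocol and SAP*

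**What the plan says.** **Allocation.** Under section 2, women were "randomly assigned to Sufentanil group (S, n=30), Ropivacaine group (R, n=30) and Sufentanil added to Ropivacaine group (SR, n=30"). Section 3 shows that the allocated component is the intrathecal injection: "2 mL of anesthetic drug as determined by her group randomization were administered into the cavity". All three arms receive an active intrathecal drug, and no untreated or epidural-only arm is described.

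**Common treatment.** Section 3 also states: "All groups received the standard epidural solution that contained 0.1% ropivacaine", with sufentanil at 0.25 µg/ml. Every woman had a "test dose of 3 ml of 1.5% lidocaine followed by an initial loading dose of 5 ml of the standard epidural solution", and a pump with the same solution was then "connected to the epidural catheter at a background continuous infusion rate of 5 mL/h". Physician boluses were allowed for breakthrough pain, with no volume or number stated. A woman counted as included only if her VAS fell below 3 at 15 minutes.

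**Primary outcome (section 5).** S/D, PI and RI in three vessels, measured "before analgesia (T_0) and 30 min (T_1), 60min (T_2), 90 min (T_3) after analgesia in the three groups".

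**Analysis (section 7).** For normally distributed measurements, a paired t "test was used for intra-group comparison and independent sample t test was used for inter-group comparison", with significance at P<0.05. The section does not rank the two comparisons, say what each is for, or say whether the between-arm test uses raw values, change from T0 or values adjusted for T0.

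**The concern.** The title asks about the effect of different labor analgesics, and the arms carry the names of the intrathecal drugs. A paired test of T0 against a later time can show that the mean index changed under the whole course of care. It cannot show that the allocated drug caused the change, because several other things changed over the same interval in every arm:

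- epidural lidocaine, ropivacaine and sufentanil were given, so the sufentanil arm also received ropivacaine and the ropivacaine arm also received sufentanil;
- the woman went from pain at about 3 cm dilatation to relief;
- labor moved on by 30 to 90 minutes.

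Since no arm lacks these elements, nothing inside one arm can separate them from the spinal drug.

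Two conclusions are at stake. One is that a significant change from T0 in an arm is an effect of that arm's drug. The other is that significance in one arm but not in another shows that the drugs differ. The design supports neither, and section 7 does not rule them out.

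**Working it through.** The plan's only sample-size figure is 90 women, 30 per arm. It comes with no effect size, SD or power, so it cannot be reproduced. The main point does not depend on it.

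**Step 1. What every arm has received by each scan.** Inputs from section 3: 3 ml of 1.5% lidocaine (15 mg/ml); a 5 ml load and 5 ml/h of solution with ropivacaine 0.1% (1 mg/ml) and sufentanil 0.25 µg/ml. Assumption: the pump starts with the load, and the scan clock starts then too.

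- Lidocaine: 3 ml × 15 mg/ml = 45 mg.
- Load alone: 5 ml × 1 mg/ml = 5 mg ropivacaine; 5 ml × 0.25 µg/ml = 1.25 µg sufentanil.
- Load plus infusion: volume = 5 + 5 × (minutes/60) ml.

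| Scan | Volume (ml) | Ropivacaine (mg) | Sufentanil (µg) |
|---|---|---|---|
| T1, 30 min | 7.5 | 7.5 | 1.875 |
| T2, 60 min | 10 | 10 | 2.5 |
| T3, 90 min | 12.5 | 12.5 | 3.125 |

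Boluses would add to this. The amounts are epidural and should not be set against the intrathecal doses as if equipotent. They show only that both study drugs are present in all arms.

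**Step 2. What each comparison estimates.** Write the mean change from T0 in arm g as (effect of spinal drug g) + C, where C covers the common epidural, pain relief and labor progress. The paired test examines whether the whole sum is zero. The difference between arms g and h is (effect of g) − (effect of h), provided C is the same in both.

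**Step 3. Illustration of disagreement between arms.** Assumptions, none of them in the documents: the spinal drugs do not differ; each arm has the same true shift d, in units of the SD of the paired differences; 30 are analysed per arm; arms are independent; the test is two-sided at 0.05. The power p of the paired t test comes from the noncentral t distribution with 29 degrees of freedom, noncentrality d√30 and critical value 2.045. The three arms disagree unless all are significant or none is, so the probability is 1 − p³ − (1 − p)³.

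| d | p per arm | p³ | (1 − p)³ | Arms disagree |
|---|---|---|---|---|
| 0.2 | 0.185 | 0.006 | 0.541 | 45% |
| 0.3 | 0.355 | 0.045 | 0.268 | 69% |
| 0.5 | 0.754 | 0.429 | 0.015 | 56% |
| 0.6 | 0.888 | 0.700 | 0.001 | 30% |
| 0.8 | 0.988 | 0.966 | 0.000 | 3% |

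With no shift at all (p = 0.05) the figure is 14%. These are rates for one index at one time. The plan has 3 vessels × 3 indexes × 3 post-baseline times = 27 such paired tests per arm.

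**Step 4. The between-arm test under the same shift.** In 40,000 simulated trials with d = 0.5 in both arms, an independent t test on the changes rejected in 5.0%, while the paired test within an arm rejected in about 76% (75% by formula). The between-arm test keeps its nominal error rate because the shared shift drops out.

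**The case against.** The strongest reply is that the valid comparison is already planned, in the same sentence as the paired test. This is a randomised trial of active regimens in women who asked for analgesia, so the lack of an untreated arm is a feature of the question. A paired test also answers a fair descriptive question: how the indexes move under the regimen as given. All of this stands. What is missing is a statement of which test carries the conclusion.

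A reader might infer that the sponsor intends to report each arm's paired result as that drug's effect. The documents do not say so. Section 7 lists tests and gives no interpretation, so the misreading is left open rather than planned.

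A reader might also infer that arms will usually disagree by chance. The documents give no SD or expected change. The rates in the table hold only under the stated assumptions, and disagreement is common only for small to moderate shifts. Exclusions after assignment (cesarean, oxytocin, failed block, VAS not below 3) leave the analysed number per arm uncertain.

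Nor should the between-arm contrast be taken as perfectly clean. Boluses given on need may differ by arm, and the allocated drug can influence who passes the VAS criterion. The shared part cancels only as far as these are similar.

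On timing, the documents do not define the zero point of the scan clock or time the load and pump start. That lidocaine and the load precede T1 follows from the order of the procedure and the 15-minute VAS check. It is the natural reading but not an explicit statement.

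Finally, the arm names could be called misleading, but section 3 discloses both the intrathecal route and the common epidural. Renaming the arms would be a matter of wording.

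**Conclusion.** The point holds in this form: section 7 leaves open which comparison answers the title question, and the within-arm paired test cannot isolate the allocated intrathecal drug. That follows from the design and needs no assumption about effect size, only the natural reading that the common epidural drugs precede T1. The 3% to 69% range for disagreement between arms over shifts of 0.2 to 0.8 SD is an illustration under assumed equal shifts, no drug difference and 30 analysed per arm.

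It should be fixed, but it does not invalidate the trial, since the between-arm comparison is already planned. What that comparison can support is the relative effect of three intrathecal regimens given with the same epidural protocol. It cannot give the effect of any of them against no analgesia.

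**What to change.** In section 7:

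1. Base all conclusions about the analgesics on the between-arm comparison of T1–T3 values adjusted for T0, by ANCOVA at each time or a mixed model over the three times.
2. Report within-arm changes descriptively, as mean change with 95% CI and no significance claim.
3. State that significance in one arm and not in another is not evidence of a difference between arms.
4. Limit conclusions to the relative effect of the three intrathecal regimens under the common epidural protocol. Note that as-needed boluses and inclusion on VAS below 3 at 15 minutes may still differ by arm, and report both by arm.

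The cost is a change to the analysis text and a slightly different model. Allocation, visits, measurements and sample size stay the same. The downside is that within-arm P values can no longer be headlined. The change does not settle multiplicity across nine indexes and three times, which needs its own provision.

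### The between-arm Doppler comparison does not adjust for the T0 value planned for every woman; ANCOVA on T0 would be more precise and needs no new data

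*Combined protocol and SAP*

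**What the plan says.** Section 5 makes the S/D, PI and RI values "of UtA, UA, MCA before analgesia (T_0) and 30 min (T_1), 60min (T_2), 90 min (T_3) after analgesia in the three groups" the primary outcomes. A pre-analgesia value of each index is therefore planned for every woman. Section 4 adds that "The above arterial blood flow indexes were measured three times and the average value was taken" and that "All doppler examinations were performed by the same sonographer".

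Section 2 has 90 women "randomly assigned to Sufentanil group (S, n=30), Ropivacaine group (R, n=30) and Sufentanil added to Ropivacaine group (SR, n=30").

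For comparing arms, Section 7 says "independent sample t test was used for inter-group comparison of measurement data conforming to normal distribution". For other data, "The measurement data with non-normal distribution were analyzed by rank sum test". It names no covariate, change score, ANCOVA or repeated-measures model. The only named test that clearly has a use for T0 is the paired t test within each arm, which does not compare drugs. Every test is read at P < 0.05.

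**The concern.** Section 7 leaves open what the between-arm test is applied to: the values at T1, T2 and T3, or the changes from T0. The wording reads most naturally as a t test on the values at each time. That ignores T0 and counts stable differences between women as noise. With 30 per arm, intervals for the drug contrasts are then wider than they need be, and a real difference in a primary index is more likely to be missed. A chance imbalance at T0 also goes uncorrected.

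Two minor points sit alongside.

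- **Role of the within-arm tests.** Paired tests within arms share the P < 0.05 rule with the between-arm test, and nothing says which one supports conclusions about the drugs. The plan does prescribe a direct between-arm test, so the role is unstated rather than wrongly stated.
- **Paired non-normal data.** The term for the non-parametric test does not say whether paired data get the signed-rank version.

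**Working it through.** The plan gives no power, effect size or SD behind its 90 women, so it has no figure to reproduce.

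**Inputs from the documents:** n = 30 per arm (Section 2); significance level 0.05 (Section 7; sidedness not stated).

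**Assumptions:** two-sided test; outcome SD = 1 at T0 and at follow-up; true difference 0.5 SD between two arms; T0-to-follow-up correlation r = 0.3, 0.5 or 0.7.

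**Standard errors of the difference between two arms**

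- Unadjusted t test: sqrt(2/30) = 0.258, 58 df, at any r.
- t test on change from T0: sqrt(2(1 − r) × 2/30), 58 df, giving 0.306, 0.258 and 0.200.
- ANCOVA: sqrt((1 − r²) × 2/30 × (1 + 1/56)), 57 df, giving 0.249, 0.226 and 0.186. The factor 1 + 1/56, with 56 = 2 × 30 − 4, is the average cost of estimating the slope on T0.

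Power is from the noncentral t distribution. The 95% half-width is the t quantile (2.002) times the standard error, for example 2.002 × 0.258 = 0.517.

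| | Unadjusted t, any r | r = 0.3 | r = 0.5 | r = 0.7 |
|---|---|---|---|---|
| Power, ANCOVA | – | 51% | 59% | 75% |
| Power, change score | – | 36% | 48% | 69% |
| Power, unadjusted t | 48% | 48% | 48% | 48% |
| 95% CI half-width, ANCOVA (SD) | 0.52 | 0.50 | 0.45 | 0.37 |
| Detectable with 80% power, ANCOVA (SD) | 0.74 | 0.71 | 0.64 | 0.53 |
| Equivalent unadjusted n per arm | 30 | 32 | 39 | 58 |

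In the second and third rows from the bottom, the second column is the unadjusted figure for comparison. The last row is 30 / ((1 − r²)(57/56)); at r = 0.5 this is 30 / (0.75 × 1.018) = 39.3.

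**Low correlation.** ANCOVA breaks even with the unadjusted test where (1 − r²)(57/56) = 1, that is r = sqrt(1/57) = 0.13. At r = 0 its power is 47.1% against 47.8%. At r = 0.2 it is 48.6%.

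**Simulation check.** With 40,000 replicates, power was 51%, 59% and 75% for two-arm ANCOVA and 48% for the t test. Rejection under no difference was about 5% throughout.

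**Skewed data.** With lognormal values and a 0.5 SD difference on the log scale (10,000 replicates), ANCOVA on logs had 51%, 59% and 76% power, against 45–46% for the rank sum test on follow-up values.

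**Chance imbalance at T0.** For one pair of arms, a T0 difference beyond 0.5 SD has probability 2 × P(Z > 0.5/0.258) = 5.3%. For at least one of the three pairs it is 13% (simulated). When the compared pair differs by 0.5 SD at T0 and the drugs do not differ, the unadjusted t test gives about 8%, 12% and 19% false positives at r = 0.3, 0.5 and 0.7. ANCOVA gives 5%.

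**The case against.** The strongest reply is that this is a choice of efficiency and not an error: the t test is valid under randomisation, and no statement in the plan becomes wrong. That is so, and it sets how serious the point is.

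The size of the gain also rests on assumptions. Neither the correlation nor a 0.5 SD effect appears in the documents. At r = 0.3 the gain is about two women per arm, and it becomes material only from about 0.5. T0 is taken in a woman asking for pain relief, while the later values follow spinal and epidural drugs. Averaging three readings steadies each session but does not make the two states alike. This stands. Against it, the risk is lopsided: nearly nothing is lost at zero correlation, and the break-even is only 0.13.

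The plan might intend changes from T0, in which case T0 is used. The text does not say so, and ANCOVA has higher power on that reading too: 51%, 59% and 75% against 36%, 48% and 69%. The benefit over the plan does then differ, being 14 points at r = 0.3 and 6 at r = 0.7.

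Two of the illustrations need care. The conditional false-positive rates are already averaged into the overall 5%, and the 13% covers any of three pairs, against 5.3% for a given one. In the lognormal example the log scale is exactly right, so part of the advantage comes from the transformation; an unadjusted t test on logs would have 48%.

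**Conclusion.** The point holds. Section 7 states no T0 adjustment for the between-arm comparison of the primary indexes, although T0 is planned for every woman. T0-adjusted ANCOVA is the better choice whether the plan means follow-up values or changes, at every assumed correlation from 0.3 to 0.7. Against the unadjusted test, the half-width falls by about 4% (0.498/0.517), 13% (0.452/0.517) and 28% (0.373/0.517) at r = 0.3, 0.5 and 0.7. These figures assume 30 analysed women per arm, equal SDs and a linear relation with T0.

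The change should be made because it is cheap and bears on the primary outcomes, not because the planned test is invalid. The two minor points are clarifications only.

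**What to change.** In Section 7, replace the between-arm t test at T1, T2 and T3 with ANCOVA adjusting for the same index at T0, on the log scale for skewed indexes, with the rule for choosing the scale written down in advance. Report each contrast with a 95% confidence interval.

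State that conclusions about the drugs rest on these contrasts, worded as the effect of the assigned intrathecal drug on top of the common epidural treatment. Report within-arm change from T0 as a mean with 95% confidence interval, labelled descriptive. Section 3 says "All patients received a test dose of 3 ml of 1.5% lidocaine followed by an initial loading dose of 5 ml", and a common epidural infusion follows, so change within an arm mixes these and the progress of labour with the assigned drug. Name the Wilcoxon signed-rank test for any paired non-normal comparison that is kept. If results have already been seen, label the adjusted analysis as added afterwards.

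The cost is SAP text and a standard model, with no new measurement. ANCOVA needs a T0 value for each woman and a roughly linear relation with T0, and gains little if the correlation is low. It does not address multiplicity: 3 indexes × 3 vessels × 3 times × 3 pairs = 81 contrasts remain. Nor does it remove bias from exclusions that appear to follow randomisation (VAS not below 3 at 15 minutes, oxytocin, caesarean section), so the adjusted contrasts are not automatically unbiased.
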